7 STUDY ASSESSMENTS

All study assessments are performed by a qualified study staff member: medical, nursing, or specialist technical staff, and are recorded in the source and eCRF, unless otherwise specified. Study assessments performed during unscheduled visits will also be recorded in the eCRF.

If the principal investigator delegates any study procedure/assessment for a subject, e.g., ECG, blood sampling etc., to an external facility, he/she should inform Actelion to whom these tasks are delegated. The set-up and oversight will be agreed upon with Actelion. The supervision of any external facilities remains under the responsibility of the principal investigator.

Calibration or service certificates for the following devices used to perform study assessments must be available prior to the enrollment of the first subject:

- Temperature measurement devices for study medication storage area and lab sample storage (i.e., freezer)
- Spirometer; in addition, a copy of the calibrations check (syringe check) of the day of measurement must be stored and a log of calibration check results must be maintained at the site [see Section 7.3.3].
- OCT
- DLCO gas analyzer; in addition, a copy of the calibrations check of the day of a test must be stored, and a log of calibration results must be maintained at the site. In addition, frequent testing involving the same healthy subject control (biological quality check) or a DLCO simulator will ensure continuous monitoring of the gas analyzer measurement accuracy over time [see Section 7.3.4].
- ECGs
- BP monitoring device

Confidential

7.1 Screening/baseline assessments

7.1.1 Informed consent (screening visit)

Prior to performing any study-specific procedures or assessments at Visit 1 (screening) or Visit 11 (Extension Treatment Period – Visit EX-1), the subject must provide written informed consent to participate in the study. If the signing of informed consent and performance of the first study-specific procedures or assessments take place on the same day, it must be clear from the source documents that informed consent was obtained prior to any study-specific procedures being performed. If a study-specific procedure or assessment has been performed as part of routine care of the subject and the results are available prior to the subject's signing of informed consent, such procedure or assessment may be used to assess eligibility and does not have to be repeated. In such cases, it must be clear from the source document when and for which reason the assessment was done prior to the signing of the informed consent.

It is the responsibility of the investigator to explain the study in all its aspects to the subject and obtain her/his informed consent. The informed consent process will be documented in the investigator site file. The language used in the oral and written information about the trial, including the informed consent form (ICF), will be provided in a language that is fully understandable to the subject.

For subjects who provide informed consent but are subsequently not enrolled into the study, the reasons for not being enrolled will be recorded in the eCRF.

7.1.2 Baseline demographics and disease characteristics

Baseline demographics (sex, age, ethnicity, body weight, and height) are to be recorded in the eCRF at Visit 1. Complete, clinically relevant medical history and current conditions are to be documented in the eCRF, as well as smoking status and disease characteristics including the date of first chronic GVHD symptoms, date of chronic GVHD diagnosis [see Section 4.5], and chronic GVHD stage and score [Appendix 2]. Complications or symptoms associated with chronic GVHD within the last 24 months prior to the study will be collected in the medical history of the eCRF.

7.1.3 Study-concomitant therapies

All study-concomitant therapy (including contraceptives and traditional and alternative medicines, i.e., plant-, animal-, or mineral-based medicines) taken by the subject from the signing of informed consent until the end of their participation in the study (i.e., EOS) will be recorded in the Concomitant Therapies pages of the eCRF. This includes all ongoing therapies and those initiated or stopped during this period. The corresponding generic name, indication, route, dose, dates of initiation and discontinuation will be recorded.

Confidential

7.2 Pharmacokinetic and pharmacodynamic assessments

These assessments are done to investigate PK and PD effects of ponesimod.

7.2.1 Pharmacokinetic assessments

7.2.1.1 *Timing for sampling*

PK samples will be collected during this study for all subjects, in order to provide information about study drug exposure in the target population.

At Visit 2 (Day 1), blood samples are collected pre-dose and then hourly (+/-20 minutes) post-dose, at the same time ECG measurements are taken, for a minimum of 4 and up to a maximum of 12 collections, depending on the number of ECG measurements taken. The ECG assessment schedule for Visit 2 (Day 1) is described in Sections 7.3.1 and 5.1.7. Placement of a peripheral venous catheter may facilitate these frequent blood collections.

Blood samples will also be collected pre-dose at Visits 3, 4, 5, 6, and 7 (Weeks 4, 8, 12, 16, and 20) and Visit 8 (EOT1). PK samples will also be drawn 3 hours (+/-20 minutes) post-dose at Visit 5 (Week 12).

7.2.1.2 *Procedures for sampling*

Up to 3 mL of blood must be collected in tubes containing ethylenediaminetetraacetic acid (EDTA). Immediately following collection of the required blood volume, the tubes must be slowly tilted backwards and forwards (no shaking) to bring the anti-coagulant into solution, and immediately cooled on ice. Within 30 minutes of collection, the tubes must be centrifuged at approximately 1500 g for 10 minutes at 2 to 8 °C. When a centrifuge that can be cooled is not available, the blood samples and the bucket of the centrifuge must be cooled on ice prior to centrifugation. The plasma must be transferred into one labeled opaque polypropylene tube to avoid carry-over of erythrocytes. All samples must be stored in an upright position at -25 °C (freezer settings: intended temperature -25 °C; upper limit -20 °C). The exact time of withdrawal of the blood sample must be entered in the eCRF, as well as the status of the subject (fed or fasted), and the time of last previous study drug intake. Blood samples for PK analysis must be drawn prior to study drug intake on the day of the visit (Visits 2, 3, 4, 5, 6, 7). Additional PK samples are drawn hourly post-dose at Visit 2. One additional PK sample is drawn 3 h post-dose at Visit 5.

To prevent degradation of ponesimod in the plasma samples, exposure to light should be minimized. After centrifugation, plasma samples should be kept in the dark.

7.2.1.3 *Labeling and shipment*

Details of the collection, labeling and shipment of the samples can be found in the laboratory manual provided to the investigator. The tubes and labels for the samples will be provided to the investigator and/or staff by the central laboratory.

Confidential

7.2.1.4 Bioanalysis

The concentration of ponesimod in plasma will be determined by a validated liquid chromatography-tandem mass spectrometry assay by Actelion, Preclinical Pharmacokinetics and Metabolism. The lower limit of quantification is 1 ng/mL.

Concentrations will be calculated by interpolation from a calibration curve. Quality control samples will be analyzed throughout the study. Their measured concentrations will be used to determine between-run and overall precision and accuracy of the analyses.

The samples will be destroyed upon signature of the Clinical Study Report.

7.2.2 Pharmacodynamic assessments

The PD marker is absolute lymphocyte counts, which will be measured as part of the hematology tests [see Section 7.3.11]. An additional PD sample will be collected at Visit 5, 3 hours (+/-20 minutes) post-dose.

At Visit 2 (Day 1), Visit 11 (EX-1) and on the day of re-initiation of study drug [see Section 5.1.8], ECGs must be performed at pre-dose and hourly thereafter for a minimum of 4 hours and up to 12 h post-dose. Subjects may be discharged from the hospital if they meet the discharge criteria before 12 h post-dose but no sooner than 4 h post-dose [see Section 5.1.7]. If the subject does not meet the defined discharge criteria at 12 hours post-dose, the cardiac safety assessor notifies the principal investigator and the subject is prematurely discontinued from ponesimod but will be kept in the hospital for observation, and additional ECG measurements will be performed until changes in ECG variables are no longer clinically relevant (i.e., discharge criteria are met [see Section 5.1.7]), or until medically indicated.

At Visit 2 (Day 1), Visit 11 (EX-1), and on the day of re-initiation of study drug where post-dose monitoring is required, significant findings – which in view of the cardiac safety assessor meet the definition of an AE and are resolved at the time of discharge of the subject – must be recorded directly on an Adverse Event page of the eCRF. All other significant findings, on Day 1, EX-1 or on the day of re-initiation of study drug where post-dose monitoring is required, that are unresolved at the time of discharge of the subject or with an onset on any other day (which in her/his view meet the definition of an AE) must be reported to the principal investigator who will record these events on the Adverse Event page of the eCRF. (The investigator may perform the function of the cardiac safety assessor if qualified, as per Section 3.4.2.)

At Visits 3, 4, 5, 6 and 7 (Weeks 4, 8, 12, 16 and 20) in the Core Treatment Period and Visits EX-2, EX-3, EX-4, EX-5, EX-6, EX-7, EX-8, EX-9, EX-10, EX-11, and EX-12 (Extension Weeks 4, 8, 12, 16, 20, 24, 36, 48, 60, 72, and 84) in the Extension Treatment Period, 12-lead ECG measurements are collected pre-dose. In the event of a grade 2 QTc elevation, a repeat 12-lead ECG must be collected 3 hours post-dose. If QTcF > 500 ms, the subject is prematurely discontinued from the study as stated in Section 5.1.10.1. In addition, a PK sample must be collected within 20 minutes after the 3 hour post-dose ECG.

Digital 12-lead ECG devices will be provided to each site by the central ECG reader for the duration of the study. Digital ECG recording must be performed for all subjects according to the study protocol schedule. The data records will be sent to the evaluation center for central reading.

Details will be provided in the ECG laboratory manual.

Confidential

7.3.2 Blood pressure

BP measurements include SBP and DBP.

BP monitoring will be performed using the same type of device throughout the study on the same arm with the subject in a fully rested supine position after the subject has been allowed to rest for a minimum of 5 minutes prior to the measurement.

At each pre-dose assessment, SBP and DBP will each be measured twice. The two obtained measurements (i.e., two SBP measurements and two DBP measurements) and the position and arm used are to be recorded in the eCRF. The means of the two obtained measurements will be calculated by the eCRF.

Post-dose assessments at Visit 2 (Day 1), Visit 11 (EX-1) and at visits for re-initiation of study drug where post-dose monitoring is required will only be measured once at each time point. This single obtained SBP measurement is to be used for determining discharge criteria on Day 1 and Visit 11 and on day of re-initiation of study drug where post-dose monitoring is required.

At Visit 2 (Day 1), Visit 11 (EX-1) and at visits for re-initiation of study drug where post-dose monitoring is required, the assessment of vital signs will be performed under the responsibility of the cardiac safety assessor who will also evaluate and interpret these assessments. At all other visits, it will be performed either under the responsibility of the cardiac safety assessor or investigator.

At Visit 2 (Day 1), Visit 11 (EX-1) and at visits for re-initiation of study drug where post-dose monitoring is required, significant findings – which in view of the cardiac safety assessor meet the definition of an AE and are resolved at the time of discharge of the subject – must be recorded directly on an Adverse Event page of the eCRF. All other significant findings, on Day 1, EX-1 or on the first day of re-initiation of study drug where post-dose monitoring is required, that are unresolved at the time of discharge of the subject or with an onset on any other day (which in her/his view meet the definition of an AE) must be recorded on the Adverse Event page of the eCRF.

BP measurements will be performed at all study visits (except FU2 – Visit 10). At Visit 2 (Day 1), Visit 11 (EX-1) and on days of re-initiation of study drug, where post-dose monitoring is required [see Section 5.1.8], SBP and DBP will be measured at pre-dose, and hourly thereafter for a minimum of 4 hours and up to 12 h post-dose. Subjects may be discharged from the hospital if they meet the discharge criteria before 12 h post-dose but no sooner than 4 h post-dose [see Section 5.1.7]. If the subject does not meet the defined discharge criteria at 12 hours post-dose, the subject will be prematurely discontinued from ponesimod but will be kept in the hospital for observation, and additional BP measurements

Confidential

will be performed until changes are no longer clinically relevant (i.e., discharge criteria are met [see Section 5.1.7]), or until medically indicated.

7.3.3 Spirometry

Spirometry tests will be performed at visits indicated in Table 1. In addition, unscheduled spirometry will have to be conducted in the event of respiratory symptoms (e.g., dyspnea).

Spirometry at Visit 1 can be performed at any time during the screening period. Spirometry at Visit 2 (Day 1) must be performed within 48 hours of the visit and prior to study drug intake. At Visits 3 and 4 (Week 4 and Week 8), spirometry may be performed up to 3 days prior to the visit date and must be performed prior to study drug intake. At Visit 5 (Week 12), spirometry may be performed up to 7 days prior to the visit date and must be performed prior to study drug intake. At Visits 8 and 23 (EOT1 and EOT2), spirometry may be performed up to 7 days prior to the visit date and no later than 7 days after the discontinuation of study drug. At all other visits indicated in Table 1, spirometry may be performed 7 days prior to or after the visit date. All spirometry assessments must be performed in the morning, preferably between 06:00 and 10:00, at approximately the same time to avoid diurnal variation.

Spirometry testing will consist primarily of assessing FEV₁ and FVC. Further parameters may be explored and/or used for spirometry quality control measures.

Spirometry tests will be conducted according to the ATS/ERS guidelines [Miller 2005a, Miller 2005b, Macintyre 2005]. The pulmonary function facility will ensure that the spirometer is functioning properly and is calibrated according to manufacturer instruction and ATS/ERS guidelines. A copy of the calibrations of the day of a test must be stored as source documents in the subject charts at each subject visit, and a log of calibration results must be maintained at the site.

Spirometry testing will be performed by a PFT technician, respiratory therapist or expert, or an equally experienced person according to the ATS/ERS guidelines [Miller 2005a] (e.g., for US, registered pulmonary function technologist and/or registered respiratory therapist). To the extent logically feasible, attempts should be made to have the same tester throughout the study for a subject, and this information will be recorded in the eCRF. Back-up testers (PFT technician, respiratory therapist, or expert or an equally qualified person according to the ATS/ERS guidelines [Miller 2005a]) may conduct spirometry if the primary tester is not available. All PFT technicians or other qualified persons participating in the studies will be trained on the specific requirements for the studies and have refreshment on ATS/ERS recommendations before study start and when compliance issues are identified.

Confidential

Subjects must refrain from taking short-acting β_2 agonists (i.e., salbutamol) for 6 hours and long-acting β_2 agonists for 24 hours prior to spirometry testing. To perform the spirometry test, subjects will be rested for a minimum of 5 minutes prior to start. Sufficient forced expiratory maneuvers (up to a maximum of eight) will be performed to produce a minimum of three technically acceptable and repeatable traces (according to ATS/ERS guideline criteria). The best (largest) FEV₁ and FVC values from the three acceptable and repeatable tests are to be selected by the PFT technician and recorded in the eCRF and will serve for the calculation of % of predicted values and used for the endpoint derivations. These values may come from separate maneuvers. The FEV₁ and FVC measures obtained at Visit 2 (Day 1) and selected as described above will be used as the study baseline.

PFT values that trigger study drug discontinuation are described in Section 5.1.10.7. Clinically relevant findings meeting the definition of an AE (new AE, or worsening of previously existing condition) [see Section 10.1.1] must be recorded on an AE page of the eCRF.

Predicted normal values for FVC and FEV₁ will be used to determine exclusion criteria as well as withdrawal criteria [see Section 5.1.10.7]. Predicted normal values will be adjusted for subjects from ethnic groups other than white/Caucasian. The formulas for the calculation of the predicted normal values for FEV₁ and FVC and the ethnic group adjustments used in this study are those of the European Community Coal and Steel [Quanjer 1993].

7.3.4 DL_{CO}

DL_{CO} tests will be performed along with spirometry [Section 7.3.3]. DL_{CO} tests will be assessed by the single breath testing technique. DL_{CO} efforts, up to a maximum of five, will be performed to produce at least two technically acceptable and repeatable traces, according to ATS/ERS guideline criteria [Macintyre 2005]. There must be a minimal interval of at least 4 minutes between each effort performed.

The average of at least two within session DL_{CO} efforts that meet the acceptability criteria are to be reported as the value for this session in the eCRF. If only one acceptable effort is achieved, this value is to be reported for this session in the eCRF. If no acceptable effort is achieved, the effort with the highest inspiratory vital capacity is to be reported in the eCRF. Reported DL_{CO} values will be entered in the eCRF, without any further adjustments.

If clinically significant alterations in DL_{CO} variables indicating a pulmonary condition that could result in increased risk for the subject are observed, he/she may be prematurely discontinued from ponesimod at the discretion of the investigator. Clinically relevant findings meeting the definition of an AE (new AE, or worsening of previously existing condition) [see Section 10.1.1] must be recorded on an AE page of the eCRF.

Confidential

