	
• Change from baseline to FU1 vs change from baseline to EOT1 in FEV₁ or FVC (absolute and % of predicted)• Change in lung diffusion capacity as assessed by diffusing capacity of lung for carbon monoxide (DLCO), expressed in absolute change and % of predicted value from baseline to all time points up to FU1• Change from baseline to FU1 vs change from baseline to EOT1 in DLCO (absolute and % of predicted)• (Serious) pulmonary AEs of special interest• Withdrawal due to pulmonary reasons/AE 
Other safety endpoints
 
• Treatment-emergent notable blood pressure abnormalities [definition in Appendix 6]• Treatment-emergent notable laboratory abnormalities [definition in Appendix 6] 
Extension Treatment Period Endpoints
 
The same endpoints will be assessed in the Extension Treatment Period as were assessed in the Core Treatment Period, however adjusted for the corresponding visit schedule.

EFFICACY ENDPOINTS	
Core Treatment Period Endpoints
 
NIH response endpoints
 
• Achievement of a partial or complete overall response at 24 weeks post-enrollment (per NIH Consensus Development Project response criteria) 
Definitions for the efficacy endpoint are based on the draft 2014 NIH Consensus Guidelines [see Appendix 7].
 
Baseline or subsequent organ abnormalities that are not due to chronic GVHD are not evaluable for response (at the organ level).
 
Complete overall response definition:
 
A complete response is defined as resolution of all reversible manifestations due to chronic GVHD in all of the following organs at the Week 24 assessment, resulting in:
 
• Skin: NIH Skin Score of 0 after previous involvement

Confidential

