4.4 Exclusion criteria

Subjects must not fulfill any of the following exclusion criteria. It is not permitted to waive any of the criteria for any subject:

Cardiovascular

1. Resting HR < 50 bpm measured by 12-lead ECG at enrollment (prior to study drug administration).
2. Myocardial infarction within 24 weeks prior to screening or ongoing unstable ischemic heart disease.
3. Cardiac failure (NYHA class III or IV) or any severe cardiac disease at time of screening.
4. History or presence of valvular heart disease associated with symptoms or hemodynamic change.
5. History or presence of cardiac rhythm disorders (e.g., sino-atrial heart block, symptomatic bradycardia, atrial flutter or atrial fibrillation, ventricular arrhythmias, cardiac arrest).

6. Presence of an increased QT corrected for HR on the basis of Fridericia's formula (QTcF) interval > 470 ms (females), > 450 ms (males) measured by 12-lead ECG at screening or pre-dose on Day 1.
7. History of syncope associated with cardiac disorders.
8. Systemic arterial hypertension not controlled by medication as judged by the investigator.

Hematologic

9. Hemoglobin (Hb) < 8.0 g/dL or need for red blood cell transfusion at screening.
10. Absolute neutrophil count $< 1.5 \times 10^9/L$ (< 1500 cells/mm 3) at screening.
11. Absolute lymphocyte count $< 0.5 \times 10^9/L$ (< 500 cells/mm 3) at screening.
12. Platelet count $< 50 \times 10^9/L$ ($< 50,000$ cells/mm 3) or need for platelet transfusion at screening.

Hepatic

13. ALT and/or AST ≥ 3.0 -fold the upper limit of normal (ULN) at screening.
14. Total bilirubin (TBL) > 1.5 -fold ULN (unless in the context of known Gilbert's Syndrome) at screening.
15. Known chronic liver or biliary disease that is not due to chronic GVHD.

Infection and infection risk

16. Active or uncontrolled bacterial, viral, or fungal infection (except onychomycosis and dermatomycosis); positive hepatitis B surface antigen or hepatitis C antibody tests at screening.
17. Cytomegalovirus (CMV) disease, including CMV pneumonia, CMV retinitis, and CMV gastroenteritis and/or subjects meeting institutional criteria for systemic therapy for CMV reactivation. (Subjects with positive CMV serology and/or CMV reactivation are not excluded if they do not have CMV disease and do not require systemic therapy.)

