7.4 Efficacy assessments

7.4.1 Organ-specific assessments (Chronic GVHD Activity Assessment Form A)

Organ-specific assessments will be performed at visits indicated in Table 1. These must be assessed by the investigator or a qualified delegate [see Section 3.4.1]. Baseline assessments are collected at Visit 2 (Day 1) before study drug is administered to the subject. Baseline or subsequent abnormalities not attributed to chronic GVHD will be recorded as AEs (if new since signing informed consent) but are not included as efficacy assessments. Organ-specific assessments are a part of the Chronic GVHD Activity Assessment eCRF. The Chronic GVHD Activity Assessment source document forms are in Appendix 7.

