11.2.2 Safety variables

The following safety endpoints/variables will be analyzed. The SAP will summarize these analyses in more detail. Safety endpoints will be analyzed from first study drug intake up to 30 days (inclusive) after last study drug intake.

Overall safety endpoints

- Treatment-emergent AEs, SAEs, and AEs of special interest
- AEs leading to premature discontinuation of study drug
- Deaths

Absolute lymphocyte count

- Treatment-emergent absolute lymphocyte count $< 0.2 \times 10^9/L$ ($< 200 \text{ cells/mm}^3$)

Cardiac rate and rhythm safety endpoints

- Treatment-emergent morphological ECG abnormalities
- Change in 12-lead ECG variables (HR, PR, QRS, QT, QTcB, QTcF) from pre-dose to selected post-dose assessments (1h, 2h, 3h, 4h) on Day 1 and on day(s) of re-initiation of study drug
- Notable abnormalities for selected 12-lead ECG variables (HR, PR, QT, QTc) at 3 h post-dose assessment on Day 1 and pre-dose on Weeks 4, 8, 12, and 24 (notable abnormalities definition in Appendix 6)
- Cardiac safety events will include:
 - Treatment-emergent QTc $> 450 \text{ ms}$ (male), $> 470 \text{ ms}$ (female), $> 500 \text{ ms}$ (male), and $> 520 \text{ ms}$ (female)
 - Treatment-emergent QTc increase from baseline $> 30 \text{ ms}$, $> 60 \text{ ms}$
 - Other treatment-emergent abnormalities observed by 12-lead ECG
 - Treatment-emergent (serious) cardiac AEs of special interest.

Confidential

Pulmonary function safety endpoints

- Treatment-emergent decrease of FEV₁ or FVC > 20% from baseline values
- Treatment-emergent decrease of percent of predicted FEV₁ or FVC > 20% from baseline values
- Change in FEV₁ and FVC from baseline, absolute and % of absolute change to all visits up to FU1
- Among subjects with a decrease of > 200 mL and > 12% in FEV₁ or FVC, respectively, from baseline to EOT1, reversibility defined as a decrease of < 200 mL and < 12% in FEV₁ or FVC, respectively, from baseline to last available follow-up
- Change from baseline to FU1 vs change from baseline to EOT1, in FEV₁ or FVC (absolute and % of predicted)
- Change in lung diffusion capacity as assessed by DL_{CO} expressed in absolute change and % of predicted value from baseline to all time points up to FU1
- Change from baseline to FU1 vs change from baseline to EOT1 in DL_{CO} (absolute and % of predicted)
- (Serious) pulmonary AEs of special interest
- Withdrawal due to pulmonary reasons/AE

Other safety endpoints

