11.2.10.4.2 Lung diffusion capacity (DLco)

Descriptive summary statistics and changes from baseline by visit will be provided for observed treatment-emergent values and changes from baseline (expressed in absolute change and % of predicted value) in DLco. In addition the DLco change from baseline to FU1 versus change from baseline to EOT1, expressed in absolute change and percent of predicted values change, will be summarized. DLco data will be analyzed in a similar manner during the Extension Treatment Period.

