Gastrointestinal-Lower GI • Diarrhea		0= no loose or liquid stools during the past week 1= occasional loose or liquid stools, on some days during the past week 2=intermittent loose or liquid stools throughout the day, on almost every day of the past week , without requiring intervention to prevent or correct volume depletion 3=voluminous diarrhea on almost every day of the past week , requiring intervention to prevent or correct volume depletion  Abnormality present but explained entirely by non-GVHD documented cause (specify): _____												
Lungs (Liters and % predicted) • Bronchiolitis Obliterans		FEV1	FVC		Single Breath DLCO (adjusted for hemoglobin)			TLC		RV		Not applicable		
		Total serum bilirubin Values from mg/dL	ULN Central Lab mg/dL	ALT Values from U/L	ULN Central Lab U/L	Alkaline Phosphatase Values from U/L	ULN Central Lab U/L							
 Abnormality present but explained entirely by non-GVHD documented cause (specify): _____														
Liver Values		Total Distance Walked and time, 2 or 6 Mins:  2 min  6 min			Karnofsky score		Platelet Count K/uL		Total WBC K/uL Values from Central Lab		Eosinophils %			
Baseline Values														

Investigator's signature _____

Confidential

5 July 2016, page 213/217

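### Section 7.3.4 and Form A give conflicting instructions on hemoglobin adjustment of DLco, and the analysis text does not say which value is used

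*Combined protocol and SAP*

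**What the plan says.** - **Recording.** Section 7.3.4 takes the average of the acceptable efforts in a session, with fallback rules when fewer are acceptable. It then says that reported DLco "values will be entered in the eCRF, without any further adjustments". It does not mention hemoglobin.
- **Form A.** The lung row of Form A in Appendix 7 has a field labelled "Single Breath DLCO (adjusted for hemoglobin". Section 7.4.1 says "Organ-specific assessments are a part of the Chronic GVHD Activity Assessment eCRF".
- **Endpoints.** Section 11.2.2 lists DLco change "expressed in absolute change and % of predicted value from baseline to all time points up to FU1". The synopsis also lists "Change from baseline to FU1 vs change from baseline to EOT1 in DLCO", and Sections 6.2.4 and 11.2.2 carry the same contrast.
- **Analysis.** Section 11.2.10.4.2 summarises "changes from baseline (expressed in absolute change and % of predicted value) in DLco" descriptively, by visit.
- **Percent predicted.** The sentence in Section 7.3.3 that begins "The formulas for the calculation of the predicted normal values for" goes on to name FEV1 and FVC only. No reference equation is given for DLco.
- **Entry.** Section 4.4 excludes "Hemoglobin (Hb) < 8.0 g/dL or need for red blood cell transfusion at screening", so milder anemia is eligible.
- **Derivations.** Section 11 leaves derivation algorithms to the SAP. The document reviewed contains none for DLco.

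**The concern.** Measured DLco depends on hemoglobin as well as on the lung, which is presumably why Form A asks for an adjusted figure. Transplant recipients on background immunosuppression may be anemic at entry, and their hemoglobin can move over 24 weeks. Without a control arm, nothing in the design separates such a shift from a drug effect.

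The contrast of FU1 with EOT1 is the most exposed. Hemoglobin that falls on treatment and recovers afterwards would look like a reversible loss of diffusing capacity. Hemoglobin that rises on treatment could hide a real loss.

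The unclear wording adds a second problem. Testing uses each site's own pulmonary function equipment, so one site may enter a corrected value and another an uncorrected one, and nothing in the record would show which.

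**Working it through.** **1. The instructions side by side.** Section 7.3.4 rules out further adjustment at entry. Form A asks for an adjusted value. Sections 11.2.2 and 11.2.10.4.2 are silent on hemoglobin. Nothing ranks one source above the other.

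**2. Could Form A supply the analysed series?** From Table 1 and Section 8:

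| Visit with DLco | Form A | Hematology |
|---|---|---|
| Screening | no | yes |
| Day 1 | yes | yes |
| Weeks 4 and 8 | no | yes |
| Week 12, EOT1 | yes | yes |
| FU1 | yes, but not after early discontinuation (Table 1, note 9) | yes |
| EX-1, EX-4, EX-7 to EX-13 | yes | yes |
| FU3 | no | yes |

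The endpoint covers all time points up to FU1. Form A has no entry at Weeks 4 and 8, none at FU1 for subjects who stopped early, and none at FU3. Only the value entered under Section 7.3.4 covers every visit.

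**3. Is hemoglobin available?** It is in the hematology panel (Section 7.3.11.2), which is scheduled at every DLco visit. It need not be taken on the same day. At Week 12, Section 8.2.4 allows each test up to 7 days either side of the visit, so the two could be up to 7 + 7 = 14 days apart.

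**4. Size.** The documents state no DLco standard deviation, threshold or expected change, no hemoglobin trajectory, and no relation between DLco and hemoglobin. There is no planned figure to reproduce. As an illustration only, assume that measured DLco changes by s% per 1 g/dL of hemoglobin while true diffusion stays constant, with s from 2 to 7. The apparent change for a hemoglobin shift of d g/dL is (1 + s/100)^d - 1.

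| Hemoglobin shift | s = 2 | s = 7 |
|---|---|---|
| -1 g/dL | 1.02^-1 - 1 = -2.0% | 1.07^-1 - 1 = -6.5% |
| -2 g/dL | 1.02^-2 - 1 = -3.9% | 1.07^-2 - 1 = -12.7% |
| +2 g/dL | 1.02^2 - 1 = +4.0% | 1.07^2 - 1 = +14.5% |

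Suppose a subject's hemoglobin falls 2 g/dL by EOT1 and is back at baseline at FU1. That subject would show an apparent DLco change of -3.9% to -12.7% at EOT1 and 0% at FU1, a pattern of reversal with no change in the lung.

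**The case against.** The strongest reply is that the text supports less than it first suggests. Much of that reply stands.

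- A reader might infer that the plan analyses unadjusted DLco. The documents do not say so. The sentence in Section 7.3.4 governs data entry, and the analysis sections are silent. "Further" may also allow a value that the site has already corrected. That reading leaves open which value each site enters.
- A reader might infer that every session will yield two different DLco entries. This is not shown. Appendix 7 reproduces NIH consensus forms, and the same lung row lists TLC and RV, which Table 1 does not schedule. Section 7.4.1.4 defines lung assessment by FEV1 and symptoms only. The DLco label may be template text, and no endpoint is stated to use it.
- A reader might infer that hemoglobin changes will appear as drug effects of a known size. Without a hemoglobin trajectory or a stated relation, neither direction nor size follows. A group mean would move by the amounts above only if the cohort's hemoglobin shifted together. Shifts in both directions would mainly add spread.
- DLco is a descriptive safety variable. It is not the primary PD endpoint, it does not define lung response, and Section 5.1.10.7 attaches no numeric trigger to it. It can still inform discontinuation at the investigator's discretion (Sections 3.4.6 and 7.3.4).

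These points limit the importance of the defect. They leave the conflict in place, along with the missing correction and the missing DLco reference equation.

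**Conclusion.** The point holds in limited form. Section 7.3.4 and Form A disagree on hemoglobin adjustment, and the analysis text neither names a correction nor says which value feeds the DLco endpoints. In a single-arm trial open to subjects with hemoglobin of 8.0 g/dL or more, hemoglobin shifts may appear as DLco change or reversal, and corrected and uncorrected values may be mixed. "Will appear" would be too strong.

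The range of about -4% to -13% for a 2 g/dL fall rests wholly on the assumed 2% to 7% per 1 g/dL and on constant true diffusion. It shows that the effect could be material, not that it is. This is a cheap improvement to a listed pulmonary safety endpoint and does not threaten the primary analysis.

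**What to change.** 1. Reconcile Section 7.3.4 with the Form A label.
2. Have sites enter the measured, uncorrected DLco and confirm on the eCRF that it is uncorrected. Ask for the same confirmation for sessions already entered. This must come before any derivation, so that no value is corrected twice.
3. In the SAP, derive hemoglobin-adjusted DLco, absolute and percent predicted, with one named correction and one named DLco reference equation. State how close in time the hemoglobin must be to the DLco test, and what is done when none falls in the window.
4. Use the adjusted value for the DLco endpoints in Sections 6.2.4, 11.2.2 and 11.2.10.4.2, and report the unadjusted value alongside.

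The cost is one added eCRF confirmation and one derivation. No new procedure is needed, because hematology is already scheduled at every DLco visit. The remaining weakness is that hemoglobin will not always be from the same day as the DLco test, most of all at Week 12.
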